6.21. Interim Analyses and Data Monitoring

A Data Monitoring Committee (DMC) will oversee the conduct of this trial. The DMC will consist of members external to Lilly. This DMC will follow the rules defined in the DMC charter, focusing on potential and identified risks for this molecule and for this class of

compounds. Data Monitoring Committee membership will include, at a minimum, specialists with expertise in rheumatology, statistics, and other appropriate specialties.

The DMC will be authorized to review unblinded results of analyses by treatment group prior to final database lock, including study discontinuation data, AEs including SAEs, clinical laboratory data, vital sign data, etc. The DMC may recommend continuation of the study, as designed; temporary suspension of enrollment; or the discontinuation of a particular dose regimen or the entire study. The DMC may request to review efficacy data to investigate the benefit/risk relationship in the context of safety observations for ongoing patients in the study. However, the study will not be stopped for positive efficacy results. Hence, no alpha is spent. Details of the DMC, including its operating characteristics, are documented in the Baricitinib Pediatric Joint DMC charter, and further details are given in the Interim Analysis Plan in Section 6.21.1.

Besides DMC members, a limited number of preidentified individuals may gain access to the limited unblinded data, as specified in the unblinding plan, prior to the interim or final database lock, to initiate the final population PK/pharmacodynamic (PD) model development processes or for preparation of regulatory documents. Information that may unblind the study during the analyses will not be reported to study sites or the blinded study team until the study has been unblinded.

A futility analysis will be conducted using the PedACR(ESR) 30 response rate observed in the first 100 patients who complete the OLLI period, this will include:

- patients who participate Safety/PK assessment period and complete OLLI period with age based final dose,
- patients who start from OLLI period and take at least 1 age-based final dose

The OLLI patients (Section 6.1.1) who discontinue early will be included. The patients who have important protocol deviations will be excluded; the detail is described in Section 6.20. The missing data imputation rule will align with Section 6.3 and Table JAHV.6.4 for PedACR(ESR) 30 response imputation. The study will stop for futility if the proportion of patient who achieve PedACR(ESR) 30 response is less than 50%. The futility analysis will be based on the observed response rate, no statistical inference will be conducted.

Unblinding details are given in Section 7.

6.21.1. Interim Analysis Plan

Analyses for the DMC will include listings and/or summaries of the following information:

- patient disposition, demographics, and baseline characteristics
- exposure
- adverse events, to include the following:
 - treatment-emergent adverse events

- serious adverse events, including deaths
- selected special safety topics
- clinical laboratory results
- vital signs
- growth parameters (for example, height, weight, assessment of bone age)

All listings will include patient ID. Summaries will include TEAEs, SAEs, special topics AEs, and treatment-emergent high and low laboratory and vital signs in terms of counts, percentages and incidence rates, where applicable. For continuous analyses, box plots of laboratory analytes will be provided by time point.

The DMC may request efficacy data if they feel there is value and to confirm a reasonable benefit/risk profile for ongoing patients in the studies. If efficacy data are requested, they will be time to disease flare and proportion of patients who are PedACR30 responders during OLLI period or proportion of patients who maintain PedACR 30 response during DBW period. Further details are given in the DMC charter.

6.22. Annual Report Analyses

Annual report analyses, such as for the Development Update Safety Report (DSUR), will be documented in a separate document.

6.23. Clinical Trial Registry Analyses

Additional analyses will be performed for the purpose of fulfilling the Clinical Trial Registry (CTR) requirements.

Analyses provided for the CTR requirements include a summary of AEs, provided as a dataset which will be converted to an XML file. Both SAEs and ‘Other’ AEs are summarized by treatment group in the DBW period, by MedDRA PT.

- An AE is considered ‘Serious’ whether or not it is a TEAE.
- An AE is considered in the ‘Other’ category if it is both a TEAE and is not serious. For each SAE and ‘Other’ AE, for each term and treatment group in the DBW period, the following are provided:
 - the number of participants at risk of an event
 - the number of participants who experienced each event term
 - the number of events experienced.
- Consistent with www.ClinicalTrials.gov requirements, ‘Other’ AEs that occur in fewer than 5% of patients/subjects in every treatment group may not be included if a 5% threshold is chosen (5% is the minimum threshold).
- Adverse event reporting is consistent with other document disclosures, for example, the CSR, manuscripts, and so forth.

Similar methods will be used to satisfy the European Clinical Trials Database (EudraCT) requirements.

7. Unblinding Plan

Refer to a separate blinding and unblinding plan document for details.

8. References

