10.3.4. Safety Analyses

Safety variables will be summarized, which include the following but are not limited to:

- Exposure to investigational product
- AEs
- SAEs
- Permanent discontinuation of investigational product
- Temporary interruption of investigation product

- AEs leading to discontinuation
- AEs of special interest
- Laboratory analytes (hematology and chemistry [including ALT and AST], neutrophil counts, and immunological measurements)
- Vital signs

Primary safety analyses will summarize baricitinib and placebo treatment groups for DBW population in DBW period. The Fisher exact test will be used for the AEs, discontinuation, and other categorical safety data for between-treatment-group comparisons in the DBW period. Continuous vital signs, body weight, and other continuous safety variables, including laboratory variables, will be analyzed using ANCOVA with treatment and baseline value in the model.

Summaries of safety data will be presented for baricitinib in OLLI period using OLLI population and throughout the study using general safety population unless otherwise stated.

Sensitivity analysis may be performed when there are patients who did not take investigational product after randomization in DBW. Pharmacokinetic analysis will be conducted using all evaluable PK data in safety/PK population. Further details will be described in the SAP.

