5.2. Determination of Sample Size

A total of 128 patients will be randomized in a 1:1 ratio to baricitinib or placebo (64 per treatment arm) in the DBW period. This sample size will provide approximately 80% power to detect the difference in time to disease flare between the 2 treatment groups using a 2-sided test with a significance level of 0.05, assuming that the expected percentages of patients experiencing disease flare in the DBW period are 35% for baricitinib and 60% for placebo and that the dropout rate is no greater than 10% in this period.

It is estimated that 197 patients are required to enter the OLLI period to allow 128 patients to be randomized into the DBW period (assuming that 65% of the patients meet the Pediatric American College of Rheumatology (PedACR) 30 criteria at the end of the OLLI period). The nonresponder and dropout rate will be monitored during the OLLI period to adjust the overall sample size to ensure that a minimum of 128 patients will be randomized in the DBW. If the

PedACR30 response rate during the OLLI period is higher than the assumed rate of 65%, fewer than 197 patients may be required.

The above sample size and power estimates are based on nQuery[®]+nTerim 4.0.

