6.18. Safety Analyses

The planned safety analyses are consistent with compound-level standards, which are based on various sources, including company standards, internal and external subject matter experts, and cross-industry initiatives (e.g., white papers produced by a PhUSE Computational Science Working Group [a collaboration with FDA and PhUSE], published in the PhUSE Deliverables Catalog). Descriptions of the safety analyses are provided in this SAP; however, some details are in compound-level safety standards.

The detail of analysis and corresponding period and population is defined in Section [6.1.1](#) and [Table JAHV.6.10](#).

Table JAHV.6.10. Summary of Safety Analysis Population, Period, Duration of Exposure and Baseline

Population for safety analysis (Section 6.1.1)	General Safety Population	DBW Safety Population	
		Baricitinib	Placebo
Treatment period	OLLI period and Safety/PK assessment period	DBW period	
Duration of study drug exposure	date of last dose of baricitinib in safety/PK assessment or OLLI period – date of first dose of baricitinib in Safety/PK assessment or OLLI period + 1	date of last dose of treatment in DBW period – date of randomization in DBW period + 1	
Baseline for LLT used in defining treatment-emergence and change from baseline analysis	Baseline period: The start of screening and ends prior to the time of first dose of bari administration. (For labs, vital signs and growth: baseline will be all scheduled and unscheduled measurements recorded during baseline period.)		

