Postbaseline for LLT used in defining treatment-emergence and change from baseline analysis	
The event start time (onset time) is on or after first dose of baricitinib in Safety/PK assessment period or OLLI period, before time of randomization in DBW period (include up to 30 days off-drug follow-up time if patient did not enter DBW period).
 
For treatment-emergent abnormal labs, vital signs and shift summaries in labs, all scheduled and unscheduled measurements will be included.
 
For change from baseline labs, vital signs and growth, only scheduled visits will be included. The early termination visits (ETV) are considered scheduled visits.
	
The event start time (onset time) is on or after time of randomization in DBW period, up to 30 days off-drug follow-up time.
 
For treatment-emergent abnormal labs, vital signs and shift summaries in labs, all scheduled and unscheduled measurements will be included.
 
For change from baseline labs, vital signs and growth, only scheduled visits will be included. The early termination visits (ETV) are considered scheduled visits.
	

Abbreviations: Bari = baricitinib; DBW = double-blind withdrawal; OLLI = open-label lead-in; JIA = juvenile idiopathic arthritis; LLT = Lowest Level Term; PK = pharmacokinetics.

Safety topics that will be addressed include the following: AEs, clinical laboratory evaluations, vital signs and physical characteristics, safety in special groups and circumstances, including adverse events of special interest (AESI) (see Section 6.18.5).

Unless otherwise specified, by-visit summaries will include planned on-treatment visits. For tables that summarize events (such as AEs, categorical lab abnormalities, shift to maximum value), post-last dose follow-up data will be included. For deaths and malignancies, all available follow-up data up to the end of the study will be included. Listings will include all safety data.

The following statistical methods will be used for safety analysis during the DBW period with the DBW safety population unless otherwise noted:

- The Fisher exact test will be used for treatment comparisons of proportions, and odds ratios with corresponding 95% confidence intervals will be provided.
- Treatment differences in mean change for continuous measurements will be assessed using an ANCOVA model fitting “baseline” as a covariate. Type 3 sums of squares will be used.

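### SAP 6.23 specifies the registry adverse-event dataset by double-blind arm only, so open-label baricitinib has no reporting group

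*SAP*

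**What the plan says.** SAP 6.23 describes an adverse-event dataset for registry posting. Serious and other "AEs are summarized by treatment group in the DBW period, by MedDRA PT". The accompanying counts (participants at risk, participants with the event, number of events) have the same scope: "for each term and treatment group in the DBW period, the following are provided". The European posting follows suit: "Similar methods will be used to satisfy the European Clinical Trials Database (EudraCT) requirements". The section also says that an event counts as serious whether or not it is treatment-emergent, and that "Adverse event reporting is consistent with other document disclosures, for example, the CSR, manuscripts, and so forth".

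Elsewhere the plan covers open-label safety. Table JAHV.6.10 in SAP 6.18 gives the General Safety Population its own column, with treatment period "OLLI period and Safety/PK assessment period". For the DBW column the event window is: "The event start time (onset time) is on or after time of randomization in DBW period, up to 30 days off-drug follow-up time". Protocol 10.3.4 states: "Summaries of safety data will be presented for baricitinib in OLLI period using OLLI population and throughout the study using general safety population".

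The planned numbers are in SAP 5.2: "It is estimated that 197 patients are required to enter the OLLI period to allow 128 patients to be randomized into the DBW period".

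**The concern.** Every child in this trial first receives baricitinib open label. Only those who are Week 12 responders go on to the DBW period. Four groups never get there:

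- PedACR30 nonresponders (Protocol 5.1.4);
- children who stop study treatment during the OLLI period (SAP 6.1.3);
- children whose age-group dose is modified after they have entered (Protocol 7.4);
- children terminated at Visit 9 because remote visits cannot supply the PedACR components (Protocol Appendix 8).

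None of them belongs to a treatment group in the DBW period, so none has a row in the dataset that SAP 6.23 describes. What is at stake is whether the registry tables represent the baricitinib experience of all treated children, or only that of responders who were still on drug at Week 12.

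**Working it through.** **1. The plan's own figure.** SAP 5.2 assumes 65% response: 128 / 0.65 = 196.9, rounded up to 197. This reproduces.

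**2. Children outside the dataset.** 197 − 128 = 69, and 69 / 197 = 35%. If only events from randomization onward are counted, the 64 placebo children also contribute no events on baricitinib: 69 + 64 = 133, and 133 / 197 = 67.5%.

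**3. Exposure share.** The documents do not give this figure. It is built from their planning inputs: 12 weeks of OLLI and up to 32 weeks of DBW (Protocol synopsis); 64 per arm, 35% flare on baricitinib and dropout of at most 10% (SAP 5.2). The added assumptions are constant hazards for flare and dropout, and a full 12-week OLLI stay.

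- Open label: 197 × 12 = 2364 patient-weeks, or 2364 × 7 / 365.25 = 45.3 patient-years.
- Combined weekly hazard in the DBW baricitinib arm: r = [−ln(0.65) − ln(0.90)] / 32.
- Mean time on treatment: [1 − exp(−32r)] / r = 24.77 weeks.
- DBW baricitinib: 64 × 24.77 = 1585 patient-weeks, or 30.4 patient-years.
- Open-label share: 2364 / (2364 + 1585) = 59.9%.

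**4. Range, one assumption changed at a time.**

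| Change | Open-label share |
|---|---|
| Add 2 weeks for 20 to 32 Safety/PK children | 60.3% to 60.5% |
| No DBW dropout (mean 26.0 weeks, 1664 patient-weeks) | 58.7% |
| All 64 stay the full 32 weeks (2048 patient-weeks) | 53.6% |
| Flare 20% to 50% | 57.5% to 62.6% |
| 10% to 35% of OLLI children stop halfway | 58.6% to 55.2% |
| Response 85% (151 enter, 23 not randomized) | 53.3% |
| Response 50% (256 enter, 128 not randomized) | 66.0% |

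The share stays above half throughout.

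**5. The two readings of the DBW limit in SAP 6.23.**

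- *It limits the events.* With the DBW window of Table JAHV.6.10, everything with onset before randomization is outside: all 69 non-randomized children, plus the open-label events of the 128 randomized ones.
- *It only names the columns.* The 69 children are still missing. Events from the first 12 weeks in randomized children would fall under the arm they later joined, so an open-label event on baricitinib could be posted under placebo. This is most plausible for serious events, which the section counts whether or not they are treatment-emergent.

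Neither reading produces an open-label baricitinib group.

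**The case against.** The strongest reply is that SAP 6.23 is not exhaustive. It says the registry analyses include this summary and nowhere excludes an open-label group. The consistency statement can be read as a harmonizing rule that would carry the CSR's open-label column into the registry. Elsewhere (for example SAP 6.18.2) the SAP uses similar DBW wording only to say where arms are compared, while open-label data are still analysed. The section cites no onset window, so it is not certain that open-label serious events in the 128 randomized children would be dropped. No test, power figure, CSR safety table or DMC review is affected.

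Much of this stands. The wording shows no intent to omit, and the consistency statement is better described as a mismatch than as proof of contradiction. But the only instruction that a programmer receives is by DBW arm, given twice. The column-label reading does not bring in the non-randomized children, and it creates an attribution problem of its own.

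A reader might infer that open-label events are kept out of public disclosure altogether. The documents do not support that: SAP 6.23 itself names the CSR and manuscripts as other disclosures, and the open-label periods are analysed under Table JAHV.6.10 and Protocol 10.3.4, including events that led to early stopping.

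**Conclusion.** The point holds for the registry and EudraCT adverse-event dataset as specified. It has no group for open-label baricitinib, about 69 of 197 children (35%) have no row, and open-label events in randomized children are either absent or open to misattribution. This should be corrected, but it does not touch the efficacy inference or the planned CSR safety tables.

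The 69 rest on the 65% response assumption and are mainly planned nonresponders; the plan gives no figure for adverse-event dropout in the OLLI period. The 60% rests on constant hazards and a full 12-week OLLI stay, and should be quoted with its range of roughly 53% to 66%.

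Two further inferences are tempting. A reader might take 60% as the share of events omitted; it is a share of exposure time, and the documents give no open-label event rate. A reader might also conclude that the posted profile is biased towards tolerability. That is plausible, because the DBW population is selected on response and on staying in treatment, but nothing in the documents measures its direction or size.

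**What to change.** In SAP 6.23:

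- Add a separate open-label baricitinib reporting group for both registries: the General safety population over the Safety/PK and OLLI periods, with the event window already set in Table JAHV.6.10. Report the same at-risk, patient and event counts as for the two DBW arms.
- State that the DBW-arm counts use the DBW event window in that table.

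The open-label window closes at randomization, or after up to 30 off-drug days for children who do not enter the DBW. The DBW window opens at randomization. Each event is therefore counted in one group only, and the consistency statement can be met. The cost is a short text change and one more run of an existing program; no efficacy analysis or alpha is affected.
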